Appendix A

o or current daily cigarette smoker	
Measured 180 days prior to drug initiation in any diagnosis/procedure position and inpatient or outpatient care setting:
 
ICD-9 Codes
 
V15.82 305.1x 984.84 CPT codes 99406, 99407, G0436, G0437, G9016, S9453, S4995, G9276, G9458, 1034F, 4004F, 4001F
 
OR dispensing of at least one nicotine or varenicline prescription: nicotine, varenicline
	
Desai, Rishi J et al. "Identification of smoking using Medicare data—a validation study of claims-based algorithms." Pharmacoepidemiology and drug safety vol. 25,4 (2016): 472-5. doi:10.1002/pds.3953

o or documented microalbuminuria or macroalbuminuria	
Measured 180 days prior to drug initiation in any diagnosis/procedure position and inpatient or outpatient care setting -
 
Proteinuria ICD 9 DX
 
791.0 ICD10 DX R80.X Albumin abnormality ICD9 Dx- 790.99 ICD10 Dx- R77.0
	
o or documented high-density lipoprotein (HDL) cholesterol of <1 mmol/l (<39 mg/dl).	N/A	
Women must be: – Postmenopausal, defined as >45 years of age with amenorrhea for at least 18 months, or >45 years of age with amenorrhea for at least 6 months and less than 18 months and a serum follicle stimulating hormone (FSH) level >40 IU/ml;	Women Age >45 years at drug initiation OR	
– or Surgically sterile (have had a hysterectomy or bilateral oophorectomy, tubal ligation), or otherwise be incapable of pregnancy,	N/A	
3 – or Heterosexually active and practicing a highly effective method of birth control, including hormonal prescription oral contraceptives, contraceptive injections, contraceptive patch, intrauterine device, double-barrier method (e.g., condoms, diaphragm, or cervical cap with spermicidal foam, cream, or gel), or male partner sterilization, consistent with local regulations regarding use of birth control methods for subjects participating in clinical trials, for the duration of their participation in the study,	
Measured 180 days prior to drug initiation in any diagnosis position and inpatient or outpatient care setting-
 
Encounter for contraceptive management ICD9: V25
 
OR
 
Non-oral contraceptives (brand names)- Depo-subQ Provera 104 Depo-Provera, generic Mirena Ortho Evra NuvaRing Implanon
 
Oral contraceptives (generic names)- See "oral contraceptives - generic" sheet.
 
Oral contraceptives (brand names)- See "oral contraceptives - generic" sheet.
	
Krumme, Alexis A, et. al. "Study protocol for the dabigatran, apixaban, rivaroxaban, edoxaban, warfarin comparative effectiveness research study." J. Comp. Eff. Res. (2018):7(1), 57-66. doi: 10.2217/cer-2017-0053.

– or Not heterosexually active. Note: subjects who are not heterosexually active at screening must agree to utilize a highly effective method of birth control if they become heterosexually active during their participation in the study.	N/A	
4 Women of childbearing potential must have a negative urine β -human chorionic gonadotropin (B-hCG) pregnancy test at screening and baseline (predose, Day 1).	N/A	One of the exclusion criteria is pregnancy, so this can be skipped.
5 Willing and able to adhere to the prohibitions and restrictions specified in this protocol.	N/A	
6 Subjects must have signed an informed consent document indicating that they understand the purpose of and procedures required for the study and are willing to participate in the study.	N/A	
7 To participate in the optional pharmacogenomic component of this study, subjects must have signed the informed consent form for pharmacogenomic research indicating willingness to participate in the pharmacogenomic component of the study (where local regulations permit). Refusal to give consent for this component does not exclude a subject from participation in the clinical study.	N/A	
8 Subjects must have taken ≥80% of their single-blind placebo capsules during the 2-week run-in period at Day 1 to be eligible for randomization.	N/A	
EXCLUSION CRITERIA		
1 History of diabetic ketoacidosis, type 1 diabetes, pancreas or beta-cell transplantation, or diabetes secondary to pancreatitis or pancrectomy.	
Measured 180 days prior to drug initiation in any diagnosis position and inpatient or outpatient care setting- DM type 1- At least 1 ICD-9 Dx code of 250.x1 or 250.x3 or ICD-10 Dx code of E10.x
 
Measured 180 days prior to drug initiation in any procedure position and inpatient or outpatient care setting- Secondary diabetes ICD-9 procedure: 249.xx Secondary diabetes
 
Measured 180 days prior to drug initiation in any diagnosis position and inpatient or outpatient care setting- Ketoacidosis 250.1x
 
Notes: We can't capture pancreas or beta-cell transplantation in claims datasets.
	
Patorno, [name] et al. "Cardiovascular outcomes associated with canagliflozin versus other non-gliflozin antidiabetic drugs: population based cohort study." BMJ 2018;360:k19 http://dx.doi.org/10.1136/bmj.k19
 
Patorno, [name] et al. "Empagliflozin and the Risk of Heart Failure Hospitalization in Routine Clinical Care: A First Analysis from the Empagliflozin Comparative Effectiveness and Safety (EMPRISE) Study." Circulation. 2019 Apr 8. doi: 10.1161/CIRCULATIONAHA.118.039177

2 On an AHA and not on a stable regimen (i.e., agents and doses) for at least 8 weeks before the screening visit and through the screening/run-in period. Note: a stable dose of insulin is defined as no change in the insulin regimen (i.e., type[s] of insulin) and ≤15% change in the total daily dose of insulin (averaged over 1 week to account for day-to-day variability).	N/A	

Appendix A

3	
– For patients on a sulfonylurea agent or on insulin: fasting fingerstick glucose at site <10 mg/dl (<6 mmol/l) at Baseline/Day 1.
 
Note: at the investigator's discretion, based upon an assessment of recent self-monitored blood glucose (SMBG) values, subjects meeting either of these fingerstick glucose exclusion criteria may continue the single-blind placebo and return to the investigational site within 14 days and may be randomized if the repeat fasting fingerstick value no longer meets the exclusion criterion. Subjects with fingerstick glucose >270 mg/dl (>15 mmol/l) may have their AHA regimen adjusted and be rescreened once on a stable regimen for at least 8 weeks.
	N/A	
4	
History of one or more severe hypoglycemic episode within 6 months before screening.
 
Note: a severe hypoglycemic episode is defined as an event that requires the help of another person.
	
Measured 180 days prior to drug initiation in primary diagnosis position and inpatient care setting:
 
ICD-9 diagnosis: 251.0, 251.1x, 251.2x, or 250.8x. If identified by 250.8x are not included if they co-occur with one of the following diagnoses: 259.8, 272.7, 681.xx, 682.xx, 686.9, 707.1x, 707.2x, 707.8, 707.9, 709.3, 730.0x, 730.1x, 730.2x, 731.8.
	
PPV 89% (ED component) – Ginde AA, Blanc PG, Lieberman RM, Camargo CA, Jr. Validation of ICD-9-CM coding algorithm for improved identification of hypoglycemia visits. BMC endocrine disorders 2008;8:4.
 
PPV 78% (inpatient component) – Schelleman H, Bilker WB, Brensinger CM, Wan F, Hennessy S. Anti-infectives and the risk of severe hypoglycemia in users of glipizide or glyburide. Clinical pharmacology and therapeutics 2010;88:214-22.

5	History of hereditary glucose/galactose malabsorption or primary renal glucosuria.	
Measured 180 days prior to drug initiation in any diagnosis position and inpatient or outpatient care setting:
 
ICD-9 diagnosis codes: 271.3x, 271.4x
	[name] suggested these codes
6	
Ongoing, inadequately controlled thyroid disorder.
 
Note: subjects on thyroid hormone-replacement therapy must be on a stable dose for at least 6 weeks before Day 1.
	N/A	
7	
Renal disease that required treatment with immunosuppressive therapy or a history of dialysis or renal transplant.
 
Note: subjects with a history of treated childhood renal disease, without sequelae, may participate.
	
Measured 180 days prior to drug initiation -
 
1. Acute renal diseases OR Chronic Renal Insufficiency in any diagnosis position and inpatient or outpatient care setting AND dispensing of an immunosuppressive agent: Acute Renal Disease 57.2x, 580.xx, 584.xx, 791.2x, 791.3x Chronic Renal Insufficiency 582.xx, 583.xx, 585.xx, 586.xx, 587.xx Immunosuppressive therapy: HCPCS codes: "36514", "80420", "C9256", "J0702", "J0704", "J1020", "J1030", "J1040", "J1094", "J1095", "J1100", "J1690", "J1700", "J1710", "J1720", "J2640", "J2650", "J2920", "J2930", "J3300", "J3301", "J3302", "J3303", "J7312", "J7506", "J7510", "J7510", "J7624", "J7637", "J7638", "J7683", "J7684", "J8540", "K0512", "K0513", "K0528", "S0173" with immunosuppressive agents in next tab "immunosuppressive agents"
 
OR
 
2. Dialysis in any diagnosis position and inpatient care setting OR Renal transplant in any diagnosis position and inpatient or outpatient care setting Codes are in the sheet 'Dialysis and Renal Transplant.'
	
Patorno, [name] et al. "Cardiovascular outcomes associated with canagliflozin versus other non-glipizid antidiabetic drugs: population based cohort study." BMJ 2018;360:k119 http://dx.doi.org/10.1136/bmj.k119
 
Patorno, [name] et al. "Empagliflozin and the Risk of Heart Failure Hospitalization in Routine Clinical Care: A First Analysis from the Empagliflozin Comparative Effectiveness and Safety (EMPRISE) Study." Circulation. 2019 Apr 8. doi: 10.1161/CIRCULATIONAHA.118.039177

8	
MI, unstable angina, revascularization procedure, or cerebrovascular accident within 3 months before screening, or a planned revascularization procedure, or history of New York Heart Association (NYHA) Class IV cardiac disease.
	
Measured 90 days prior to drug initiation in any diagnosis/procedure position and care setting defined below-
 
Any of the following codes in inpatient or outpatient care setting:
 
MI ICD-9 diagnosis 410.xx Unstable angina ICD-9 diagnosis 411.xx Left ventricular assist CPT-4 33990-33993 Stroke ICD-9 diagnosis: 430.xx, 431.xx, 433.x1, 434.x1, 436.x Carotid bypass: ICD9 procedure: 39.28 TIA 435.xx Peripheral arterial stenting or surgical revascularization ICD-9 39.25, 39.50, 39.99. PTCA: Inpatient CPT-4: 92973, 92982, 92984, 92995, 92996, 92920-92921, 92924-92925, 92937, 92938, 92941, 92943, 92944 OR - Inpatient or outpatient - ICD-9 procedure: 00.66, 36.01, 36.02, 36.03, 36.05, 36.09 Stenting: Inpatient CPT-4: 92980, 92981, 92928-92929, 92933 - 92934 -OR -Inpatient or outpatient - ICD-9 procedure: 36.06, 36.07 CABG: Inpatient CPT-4: 33510-33536, 33545, 33572 -OR -Inpatient or outpatient - ICD-9 procedure: 36.1x, 36.2x Transmyocardial revascularization: Inpatient or Outpatient CPT-4: 33140, 33141 OR -Inpatient or outpatient ICD-9 procedure: 36.31-36.34
	
Patorno, [name] et al. "Cardiovascular outcomes associated with canagliflozin versus other non-glipizid antidiabetic drugs: population based cohort study." BMJ 2018;360:k119 http://dx.doi.org/10.1136/bmj.k119
 
Patorno, [name] et al. "Empagliflozin and the Risk of Heart Failure Hospitalization in Routine Clinical Care: A First Analysis from the Empagliflozin Comparative Effectiveness and Safety (EMPRISE) Study." Circulation. 2019 Apr 8. doi: 10.1161/CIRCULATIONAHA.118.039177
 
Left Ventricular Assist Codes from - http://www.hcpro.com/HIM-289708-859/Tip-Note-new-codes-for-ventricular-assist-devices.html

9	
Findings on 12-lead electrocardiogram (ECG) that would require urgent diagnostic evaluation or intervention (e.g., new clinically important arrhythmia or conduction disturbance).
	
Measured 180 days prior to drug initiation in primary diagnosis position and inpatient care setting:
 
Cardiac conduction disorders ICD 9: 426.xx Other cardiac dysrhythmia ICD 9: 427.xx, exclude 427.5x (cardiac arrest) and 427.3x And, 427.6x
	
Patorno, [name] et al. "Cardiovascular outcomes associated with canagliflozin versus other non-glipizid antidiabetic drugs: population based cohort study." BMJ 2018;360:k119 http://dx.doi.org/10.1136/bmj.k119
 
Patorno, [name] et al. "Empagliflozin and the Risk of Heart Failure Hospitalization in Routine Clinical Care: A First Analysis from the Empagliflozin Comparative Effectiveness and Safety (EMPRISE) Study." Circulation. 2019 Apr 8. doi: 10.1161/CIRCULATIONAHA.118.039177

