22	Current use of a corticosteroid medication or immunosuppressive agent, or likely to require treatment with a corticosteroid medication (for longer than 2 weeks in duration) or an immunosuppressive agent. Note: subjects using inhaled, intranasal, intra-articular, or topical corticosteroids, or corticosteroids in therapeutic replacement doses may participate.	Measured 180 days prior to drug initiation as a dispensing of one of the following drugs- Systemic corticosteroids (With Route of Administration is intravenous)- Cortisone, hydrocortisone, prednisone, prednisolone, methylprednisolone, triamcinolone, dexamethasone, betamethasone. immunosuppressive agents o RA, AS, and PsA: methotrexate, hydroxychloroquine, azathioprine, cyclosporine, leflunomide, minocycline, sulfasalazine. o SLE: hydroxychloroquine, azathioprine, mycophenolate mofetil. o IBD: azathioprine, mercaptopurine	Patorno, [name] et al. "Cardiovascular outcomes associated with canagliflozin versus other non-glipizid antidiabetic drugs: population based cohort study." BMJ 2018;360:k119 http://dx.doi.org/10.1136/bmj.k119 Patorno, [name] et al. "Empagliflozin and the Risk of Heart Failure Hospitalization in Routine Clinical Care: A First Analysis from the Empagliflozin Comparative Effectiveness and Safety (EMPRISE) Study." Circulation . 2019 Apr 8. doi: 10.1161/CIRCULATIONAHA.118.039177 Desai, Rishi et al. "Risk of serious infections associated with use of immunosuppressive agents in pregnant women with autoimmune inflammatory conditions: cohort study" BMJ 2017; 356 doi: https://doi.org/10.1136/bmj.j895
23	Received an active investigational drug (including vaccines) or used an investigational medical device within 3 months before Day 1/baseline or received at least one dose of canagliflozin in a prior study.	Already applied based on the canagliflozin and comparator washout, but measured again 90 days prior to drug initiation as a dispensing for canagliflozin	

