Appendix A

Immunosuppressive agents
ALEMTUZUMAB
BETAMETHASONE
BETAMETHASONE ACETATE/BETAMETHASONE SODIUM PHOSPHATE
BETAMETHASONE DIPROPIONATE
BETAMETHASONE DIPROPIONATE/PROPYLENE GLYCOL
BETAMETHASONE SODIUM PHOSPHATE
BETAMETHASONE VALERATE
BUDESONIDE
BUDESONIDE, MICRONIZED
CORTISONE ACETATE
DEXAMETHASONE
DEXAMETHASONE ACETATE
DEXAMETHASONE ACETATE, MICRONIZED
DEXAMETHASONE ISONICOTINATE
DEXAMETHASONE PHOSPHATE
DEXAMETHASONE SOD PHOSPHATE
DEXAMETHASONE SODIUM PHOSPHATE IN 0.9 % SODIUM CHLORIDE
DEXAMETHASONE SODIUM PHOSPHATE/PF
DEXAMETHASONE, MICRONIZED
HYDROCORTISONE
HYDROCORTISONE ACETATE
HYDROCORTISONE CYPIONATE
HYDROCORTISONE SOD PHOSPHATE
HYDROCORTISONE SOD SUCCINATE
IMMUNE GLOBULIN, BOVINE/PLASMA PROTEIN FRACTION, BOVINE
IMMUNE GLOBULIN, GAMM(IGG)/GLYCINE/GLUCOSE/IGA 0 TO 50 MCG/ML
IMMUNE GLOBULIN, GAMM(IGG)/GLYCINE/IGA GREATER THAN 50 MCG/ML
IMMUNE GLOBULIN, GAMM(IGG)/MALTOSIDE/IGA GREATER THAN 50 MCG/ML
IMMUNE GLOBULIN, GAMM(IGG)/SORBITOL/GLYCIN/IGA 0 TO 50 MCG/ML
IMMUNE GLOBULIN, GAMM(IGG)/SUCROSE/IGA GREATER THAN 50 MCG/ML
IMMUNE GLOBULIN, GAMMA (IGG)/GLYCINE/IGA 0 TO 50 MCG/ML
IMMUNE GLOBULIN, GAMMA (IGG)/PROLINE/IGA 0 TO 50 MCG/ML

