Appendix A

IMMUNE GLOBULIN, GAMMA (IGG)/SORBITOL/IGA 0 TO 50 MCG/ML
LYMPHOCYTE IG, ANTITHYMOCYTE/THIMEROSAL
LYMPHOCYTE IMMUNE GLOBULIN, ANTITHYMOCYTE (EQUINE)
METHYLPREDNISOLONE
METHYLPREDNISOLONE ACETATE
METHYLPREDNISOLONE ACETATE, MICRONIZED
METHYLPREDNISOLONE SODIUM SUCCINATE
METHYLPREDNISOLONE SODIUM SUCCINATE/PF
METHYLPREDNISOLONE, MICRONIZED
PREDNISOLONE
PREDNISOLONE ACETATE
PREDNISOLONE ACETATE, MICRONIZED
PREDNISOLONE SOD PHOSPHATE
PREDNISOLONE, MICRONIZED
PREDNISONE
PREDNISONE MICRONIZED
RITUXIMAB
RITUXIMAB/HYALURONIDASE, HUMAN RECOMBINANT
TRIAMCINOLONE
TRIAMCINOLONE DIACETATE
TRIAMCINOLONE HEXACETONIDE
TRIAMCINOLONE HEXACETONIDE, MICRONIZED
AZATHIOPRINE
AZATHIOPRINE SODIUM
CYCLOSPORINE
CYCLOSPORINE, MODIFIED
HYDROXYCHLOROQUINE SULFATE
LEFLUNOMIDE
MERCAPTOPURINE
MINOCYCLINE HCL
MINOCYCLINE HCL MICROSPHERES
MINOCYCLINE HCL/EMOL COMB NO.16/SKIN CLNSR L4/TOP AGENT NO.3
MINOCYCLINE HCL/EYELID CLEANSER COMBINATION NO. 1
MINOCYCLINE HCL/WIPES WITH SKIN CLEANSER NO.4
MYCOPHENOLATE MOFETIL
MYCOPHENOLATE MOFETIL HCl

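### Exclusion 7 sets no route, duration or indication limit on its drug sheet, so as written a renal code plus a topical or inhaled corticosteroid would exclude a patient

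*Combined protocol and SAP*

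**What the plan says.** The trial criterion behind Exclusion 7 in Appendix A is "Renal disease that required treatment with immunosuppressive therapy or a history of dialysis or renal transplant". The claims version has two arms.

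- **Drug arm.** "Acute renal diseases OR Chronic Renal Insufficiency in any diagnosis position and inpatient or outpatient care setting AND dispensing of an immunosuppressive agent", within 180 days before initiation. The agents are defined by a list of HCPCS codes "with immunosuppressive agents in next tab".
- **Dialysis or transplant arm.** "Dialysis in any diagnosis position and inpatient care setting OR Renal transplant in any diagnosis position".

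The sheet of immunosuppressive agents in Appendix A is a list of generic names with no route column. It includes entries such as "BETAMETHASONE DIPROPIONATE/PROPYLENE GLYCOL", betamethasone valerate, hydrocortisone, budesonide and prednisone. It also lists minocycline, both plain and as kits, for example "MINOCYCLINE HCL/WIPES WITH SKIN CLEANSER NO.4".

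Exclusion 22 treats corticosteroids differently. Its trial text states that "subjects using inhaled, intranasal, intra-articular, or topical corticosteroids, or corticosteroids in therapeutic replacement doses may participate", and its claims version counts the listed systemic corticosteroids only when the route is intravenous. Exclusion 22 also names minocycline among its immunosuppressive agents.

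The flowcharts in section 5.3 report Exclusion 7 as a single line, without separating the two arms.

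**The concern.** The trial excluded people whose kidney disease itself called for immunosuppression. The drug arm asks only that a renal code and a listed drug both appear within 180 days. Nothing connects the drug to the kidney disease, and nothing restricts how it was given.

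Two patients with the same steroid cream are therefore treated differently. The one with a renal code leaves at Exclusion 7. The one without it stays, because Exclusion 22 does not count the cream.

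Section 5.2.2 says the criteria follow the trial as closely as possible. The literal rule would remove some trial-eligible renal patients for an unrelated prescription, and a reader could not rebuild the cohort with confidence.

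**Working it through.** **1. The flowchart counts (section 5.3).** Patients before Exclusion 7 minus patients removed should equal patients remaining.

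| Cohort | Database | Before | Removed | Remaining | Removed, % |
|---|---|---|---|---|---|
| DPP4i | Optum | 132,390 | 1,512 | 130,878 | 1.14 |
| DPP4i | MarketScan | 140,649 | 662 | 139,987 | 0.47 |
| DPP4i | Medicare | 356,379 | 6,367 | 350,012 | 1.79 |
| SU | Optum | 196,845 | 2,276 | 194,569 | 1.16 |
| SU | MarketScan | 175,623 | 976 | 174,647 | 0.56 |
| SU | Medicare | 497,275 | 9,763 | 487,512 | 1.96 |

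All six subtractions are exact. Totals:
- DPP4i: 1,512 + 662 + 6,367 = 8,541, and 8,541 / 629,418 = 1.36%.
- SU: 2,276 + 976 + 9,763 = 13,015, and 13,015 / 869,743 = 1.50%.

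These are ceilings, because the line also holds dialysis, transplant and genuine immunosuppression. Exclusion 7 is the seventh largest numbered exclusion in each cohort. In the DPP4i cohort it follows Exclusions 14 (27,850), 1 (25,491), 22 (15,305), 8 (12,497), 16 (10,797) and 10 (10,087).

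**2. Was the literal rule run?** The sheet includes prednisone, so a literal rule would catch renal patients on oral steroids. Let R be the patients with chronic renal insufficiency left in the unmatched cohort, and p the prevalence of oral corticosteroid use left there (both from Appendix B, Table 1, arms added). If renal patients used oral steroids at the cohort average, expected removals are R × p / (1 − p). For the DPP4i cohort:
- Optum: R = 17,268 + 1,743 = 19,011; p = 13,909 / 114,319 = 0.1217; expected 2,633, reported 1,512.
- MarketScan: R = 8,845; p = 0.1145; expected 1,143, reported 662.
- Medicare: R = 51,805; p = 0.1393; expected 8,386, reported 6,367.

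The total is about 12,160. Scaled back to the Exclusion 7 step by the ratio of patients remaining there to the final cohort, it is about 14,240. The reported total is 8,541, with dialysis and transplant included. The same calculation for the SU cohort gives about 15,780 (18,260 scaled) against 13,015.

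This rests on the equal-prevalence assumption. Without scaling, the reported DPP4i count would fit a literal rule only if oral steroid use among renal patients were at most 8,541 / (79,661 + 8,541) = 9.7%, against 69,265 / 534,113 = 13.0% in the cohort. For SU the figures are 13,015 / (104,523 + 13,015) = 11.1% against 95,784 / 742,817 = 12.9%. The counts suggest a narrower rule was run but do not prove it.

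**3. Power (section 10, pooled DPP4i superiority).** Power = Φ(|ln HR| × √(events / 4) − 1.96).
- As planned: events = 2 × 76,101 × 12.65 / 1,000 = 1,925.36; 0.1508 × 21.94 − 1.96 = 1.349; power 0.911, which matches the plan.
- Restoring all 8,541 pro rata: events rise by the factor 1 + 8,541 / 620,877 = 1.0138, and power becomes about 0.915.

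**The case against.** Several points on the other side stand.

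- **Minocycline.** A reader might infer that minocycline users with renal disease are wrongly lost at Exclusion 7. Exclusion 22 removes anyone dispensed minocycline in the same 180 days, with or without a renal code. Deleting it from Exclusion 7 alone returns no one to the final cohort.
- **Proof of misclassification.** A reader might infer that patients have in fact been wrongly excluded. The documents do not show this. The word joining the HCPCS list to the sheet could mean AND or OR, the counts are below what the literal rule would be expected to give, and Appendix A refers readers to a shared folder for missing detail that is not reproduced. That betamethasone or budesonide entries cover topical or inhaled products is general drug knowledge. What the document shows is that no route is given.
- **Bias between arms.** A reader might infer confounding from the unmatched prevalence of chronic renal insufficiency, 16.3% for DPP4i and 7.5% for canagliflozin. The rule is a baseline exclusion applied identically to both groups before matching. After matching the figures are 7.7% and 7.9%.
- **Trial eligibility of those removed.** The trial's eGFR limit (Exclusion 12) could not be applied and the renal codes carry no stage limit. Some patients removed may have been trial-ineligible anyway.
- **Indication.** A route limit would not link the drug to the kidney disease. A renal patient given oral prednisone for something else would still be excluded.

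None of this closes the gap in the text. If the literal rule ran, it removes patients the trial would have accepted. If a narrower rule ran, the protocol does not describe it.

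**Conclusion.** The point holds as a minor specification fault. As written, Exclusion 7 counts any dispensing from a sheet without route, duration or indication limits, which departs from its own trial criterion and is inconsistent with Exclusion 22. The number of patients affected cannot be computed from the documents. It lies between zero and the whole line (8,541 for DPP4i, 13,015 for SU), and must be below that ceiling to the extent that the line reflects dialysis, transplant and genuine immunosuppression. Power is essentially unchanged. The consequence is for how closely the cohort mirrors the trial and whether it can be reproduced. The documents do not support a claim of bias in the matched comparison.

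**What to change.** 1. In Exclusion 7, limit the corticosteroid entries by route so that the products exempted in the Exclusion 22 trial text (inhaled, intranasal, intra-articular, topical) do not count.
2. State whether the HCPCS list and the drug sheet are joined by AND or OR.
3. Reconcile the minocycline entries in Exclusions 7 and 22 together.
4. Rerun the flowchart with drug-triggered removals and dialysis or transplant removals on separate rows.
5. Acknowledge that the drug's indication is still not established by the rule.

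The cost is a code-list edit and a rerun of cohort assembly and matching, with no new data. If a narrower rule was already run, correcting the text to match it and splitting the count is enough.
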